6.2.2 Randomization

This study is randomized and double-blinded. Randomized treatment assignments will be generated by the Rockefeller University Hospital pharmacy. The 8 participants in each group will be randomized in a ratio of 6 study drug recipients to 2 placebo recipients. Randomization will be generated using SAS 9.4. Blinding will not apply to the assignment of dose levels (3 or 10 mg/kg). The study preparation will be provided to the study nurses for injection under a coded, masked identification. The placebo and mAb preparations will be indistinguishable in the preparation provided for participants. The nurses, study staff, investigators, and participants will be blinded as to the identity of the study preparation. Participants will be unblinded at the end of the study. To accomplish this, study nurses will be provided with the randomization code after the study has been completed, and they will notify each participant. In the event of a medical emergency wherein knowledge of the treatment assignment will influence the participant's care, the Principal Investigator may unblind the treatment assignment.

6.2.3 3BNC117 and 10-1074 Administration Procedure

3BNC117 is provided in single-use vials containing 5 ml of the product at a concentration of 20 mg/ml. The volume of 3BNC117 to be administered will be calculated by the site research pharmacist, according to study assignment. The appropriate volume of 3BNC117 will be diluted in sterile normal saline to a total volume of 100 ml, and will be administered as an intravenous infusion over 60 minutes.

10-1074 will be provided in single-use vials containing 5 ml of the product at a concentration of 20 mg/ml. The volume of 10-1074 to be administered will be calculated by the RUH research pharmacist, according to study assignment. The appropriate volume of 10-1074 will be diluted in sterile normal saline to a total volume of 100 ml and will be administered as a slow intravenous infusion over 60 minutes.

- Sterile saline, NaCl 0.9% (placebo) will be dispensed in a volume of 100 ml, and will be administered as a slow intravenous infusion over 60 minutes. A second bag of sterile saline will be administered after the infusion of the first saline bag is completed and the line is flushed.

Both antibodies will be administered intravenously, via a peripheral vein in one of the upper extremities. The administration site should be free of potentially complicating dermatologic conditions. At the end of infusion, the IV line will be flushed with 20 ml of normal saline to ensure all the medication has been delivered.

6.2.4 Medical History and Physical Examination

At the time of screening, participant's past medical history will be collected and will include details of any previous reaction to vaccination, and contraceptive practices. Interim medical histories will be collected at time-points according to the Time of Events Schedule (**Appendix A**).

A general physical examination will be conducted including weight, height, vital signs, and examination of skin, respiratory, cardiovascular, central nervous and abdominal systems. At the time of the first 3BNC117 and 10-1074 infusions and at selected time-points thereafter, general and/or directed physical examinations will be performed according to the Time of Events Schedule (**Appendix A**). A directed physical examination will include vital signs, examination of infusion site, and any further examination indicated by history or observation.

6.2.5 Blood Collection, Storage and Shipment

Venous blood will be collected at every study visit according to the Time of Events Schedule (**Appendix A**). At no time will the total volume of blood collected exceed 550 ml over an 8-week period. All specimens will be handled according to SOPs that were developed in the Processing Lab within the Laboratory of Molecular Immunology. Frozen PBMCs, plasma and serum will be processed and stored in the Laboratory of Molecular Immunology.

6.2.6 HIV testing and Counseling

Study personnel will assess participants for past and current risk of HIV infection and counsel them prior to collecting blood for an HIV test. Study personnel will perform post HIV-test counseling as indicated in the Time of Events Schedule (**Appendix A**). The counseling process will include information on HIV, safe sex practices and risk reduction. The objective of counseling is to ensure that participants have sufficient knowledge about HIV infection to understand the purpose of the test, the implications of a positive or negative result and the standard of care available locally for HIV infection. Additionally, risk reduction counseling, including safe-sex counseling, will be provided during the study to reinforce low-risk behavior.

6.2.7 HIV Infection

Participants who are found to be HIV-infected at screening and participants who acquire HIV infection during the trial will be withdrawn from the study and managed in the following way:

a) The participant will be counseled by the study investigators. The counseling process will assist the participant with issues such as: psychological and social implications of HIV infection; whom to inform and what to say; implications for sexual partners and avoidance of transmission to others in the future.

b) The participant will then be referred to a patient support center or institution of his/her choice for a full discussion of the clinical aspects of HIV infection. Referral will be made to a designated physician or center for discussion of options of treatment of HIV infection.

6.2.8 Monitoring for cytokine release associated adverse events and treatment of cytokine release syndrome

Based on previous clinical experience, it is unlikely that administration of 3BNC117 or 10-1074 will lead to cytokine release syndrome. However, a potential side effect of a monoclonal antibody can be the stimulation of a massive release of cellular cytokines, which can have profound effects on blood pressure, vascular integrity, and myocardial, lung, liver, and kidney functions. If cytokine release syndrome occurs, the participant may need to be treated with intravenous fluids, vasopressors, and high-dose corticosteroids and may require ventilatory support.

Following the completion of the second infusion, participants enrolled in group 1 will be observed for 4 hours and participants enrolled in groups 2 and 3 will be observed for 1 hour. Access to a twenty-four hour on-call physician is available. The RUH outpatient and inpatient units are equipped with crash carts for immediate medical care, should the need

arise. In case of an emergency, after stabilization of the participant, he/she will be transferred to the neighboring tertiary care center, New York Presbyterian Hospital (Cornell) for specialized medical care.

6.2.9 Family Planning Counseling

During screening and subsequent study visits, study personnel will counsel participants about the importance of prevention of pregnancies and the use of condoms, as well as other effective family planning methods. Condoms will be provided.

Study participants participating in sexual activity that could lead to pregnancy will be advised to use two effective methods of contraception (i.e. condom with spermicide, diaphragm with spermicide, hormone-eluting IUD, hormone-based contraceptive with condom) for the duration of the study.

6.2.10 Reimbursement

Participants will be compensated \$25 for the initial screening visit.

They will be compensated:

- \$200 for each infusion visit
- \$80 for each post infusion follow up visit
- \$100 for the final study visit
- \$50 for each eye exam

At the Rockefeller site, payment will be made to participants who fill out a form from The Rockefeller University Finance Office and are eligible for and want to receive payment.

In Group 1, participants who complete all study visits will receive a total of \$1065 throughout the study.

In Groups 2 and 3, participants who complete all study visits will receive a total of \$2,105 throughout the study.

If a member of the study team asks a participant to return for an unscheduled visit, the participant will be compensated \$25 each time.

Compensation is provided to help cover their travel expenses, as well as child care and time lost from gainful employment. Participants will be compensated only for the visits they complete.

6.2.11 Safety Assessments

6.2.11.1 Solicited Adverse Events

Solicited adverse events in this study include presence of feverishness, chills, headache, nausea, vomiting, malaise, myalgia and arthralgia occurring in the first 7 days following 3BNC117 and 10-1074 infusions, as well as infusion site reaction or effects caused by extravasation.

Solicited adverse events will be collected prospectively by structured interviews on infusion and post-infusion follow up visits; recorded and graded according to preestablished criteria. The Toxicity Grading Scale for Healthy Adult and Adolescent Volunteers Enrolled in Preventive Vaccine Clinical Trials (2007) will be used to grade adverse events (see **Appendix B**). In addition, the Common Terminology Criteria for Adverse Events (CTCAE) v4.03 grading scale will be used for reporting and grading adverse events related to infusion reactions and cytokine release syndromes in all groups.

Vital signs (pulse, respiratory rate, blood pressure and temperature) will be measured prior to each antibody administration, at the end, 1 hour and 4 hours (group 1 only) after the second infusion is completed, graded according to **Appendix B** and recorded. All medications required for treatment of adverse events will be recorded.

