3.3.3 Preclinical Toxicity Studies with 3BNC117

3.3.4 Clinical Experience with 3BNC117

3BNC117 was evaluated in a phase 1 study in both HIV-uninfected and HIV-infected participants (protocol MCA-835) and is currently being tested in two ongoing exploratory phase 2a studies in HIV-infected participants (protocols MCA-867 and MCA-866).

In protocol MCA-835, study participants were administered one or two intravenous infusions of 3BNC117 at increasing dose levels (1 mg/kg, 3 mg/kg, 10 mg/kg or 30 mg/kg), and were followed for 24 weeks after last infusion. In total, 55 participants (22 HIV-uninfected, 17 viremic HIV-infected and 16 ART-treated HIV-infected individuals) were enrolled in the study. Five HIV-uninfected individuals received two infusions of 3BNC117 at 30 mg/kg, 12 weeks apart. Twenty-two participants (3 HIV-uninfected and 19 HIV-infected) were administered one dose of 30 mg/kg.

Overall, 3BNC117 was generally safe and well-tolerated, mild transient myalgia, fatigue and headache were the most commonly reported adverse events (AEs). Some participants reported ophthalmic complaints, but a causal relationship with 3BNC117 was not established. No SAEs or grade 3/4 AEs deemed related to 3BNC117 occurred. A safety data summary is included in the Investigator's Brochure (IB).

Preliminary PK data show that 3BNC117's half-life is 17.6 days in HIV-uninfected and 9.6 days in viremic HIV-infected individuals. 3BNC117 decay rates following first and second infusions appear to be similar.

When administered at 30 mg/kg, 3BNC117 induced rapid decreases in plasma HIV-1 RNA levels that varied between individuals from 0.8 to 2.5 log₁₀ copies/ml. The median time to reach the nadir in viremia was 7 days, and the mean drop in VL was 1.48 log₁₀ copies/ml at nadir. Emergence of resistant viral strains was variable, with some individuals remaining sensitive to 3BNC117 for a period of 28 days after infusion (Caskey, Klein et al. 2015).

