3.4.3 Preclinical Toxicity Studies with 10-1074

3.4.4 Clinical Experience with 10-1074

10-1074 is being evaluated in a phase 1 study in both HIV-uninfected and HIV-infected participants (protocol MCA-885). Study participants are administered one intravenous infusion of 10-1074 at increasing dose levels (3 mg/kg, 10 mg/kg or 30 mg/kg), and are followed for 24 weeks after infusion.

As of 12 January 2016, 23 participants (12 HIV-uninfected, 8 viremic HIV-infected and 3 ART-treated HIV-infected individuals) have enrolled in the study. Eleven participants (6 HIV-uninfected and 5 HIV-infected) were administered one dose of 30 mg/kg. 10-1074 has been generally safe and well tolerated at all doses tested. Most common reported adverse event reported to data was fatigue.

Preliminary pharmacokinetics data show that 10-1074's half-life in HIV-uninfected individuals is approximately 15.5 days. Similarly to 3BNC117, 10-1074 has been generally safe and well-tolerated. When administered at 10 mg/kg, 10-1074 reduced plasma viremia by an average of 1.38 log₁₀ copies/ml (n = 3, range 1 – 1.56 log₁₀ copies/ml). At 30 mg/kg, 10-1074 led to similar decline in plasma HIV-1 RNA in the 4 out of 5 participants enrolled to date (n = 4, average 1.37 log₁₀, range 1 – 1.7 log₁₀ copies/ml). One participant dosed at 30 mg/kg experienced a 0.4 log₁₀ decline in viremia. The baseline sensitivity of this participant's plasma viruses to 10-1074 is not yet known. The study remains open to enrollment, and safety, PK and antiretroviral activity data are being collected.

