3.6 Outcomes

Primary Outcomes:

- The rate of signs, symptoms and laboratory abnormalities, in addition to local and systemic reactogenicity adverse events 1 week after the combination of 3BNC117 and 10-1074 infusion in all study groups.
- The pharmacokinetic profile of 3BNC117 and 10-1074: elimination half-life (t_{1/2}), clearance (CL/F), volume of distribution (Vz/F), AUC and decay curve in all study groups.

Secondary Outcomes:

- Frequency and levels of induced anti-3BNC117 and anti-10-1074 antibodies at 8 weeks after each infusion in all study groups.
- The rate of signs, symptoms and laboratory abnormalities that occur during study follow up after 3BNC117 and 10-1074 infusions in all study groups.

Exploratory Outcome:

- Neutralization activity of serum from study participants against a panel of viruses as measured by the TZM.bl neutralization assay.

[figure not shown]
4 Study Design

This is a phase 1 clinical trial to evaluate the safety and pharmacokinetics of the highly neutralizing anti-HIV-1 monoclonal antibodies 3BNC117 and 10-1074, when given in combination, in HIV-uninfected individuals. This study is intended to support the development of the combination of 3BNC117 and 10-1074 mAbs for use as prophylaxis against HIV infection in healthy HIV-uninfected individuals at risk for HIV infection.

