- In the cross-reactivity study in human tissues, 3BNC117 stained rare cells in the conjunctival recesses. When rats were administered 3BNC117, ocular toxicity was not observed. Sixty-eight participants have received 3BNC117 to date, and 12 participants reported mild ophthalmic complaints (such as pruritus, conjunctival erythema, increased lacrimation) during study follow up. In all instances symptoms resolved without specific treatment and ophthalmologic evaluations 5 months after 3BNC117 administration did not show changes from baseline.
- In the cross-reactivity study in human tissues, 10-1074 stained the cytoplasm of nerve cells in the optic nerve of the eye. Twenty-two participants have received 10-1074 to date. One participant reported transient and mild dryness in the eyes.
- Participants might have false positive HIV serology results after 3BNC117 and 10-1074 administration. This will likely be temporary, while antibody levels are detectable in blood.
- The adverse effects of 3BNC117 and 10-1074 to a fetus or unborn child are unknown.

Other potential risks

- Blood drawing and phlebotomy can be associated with pain, bruising, anemia or infection at the site of venipuncture. Rarely, fainting may follow phlebotomy.
- Participants may engage in increased risk taking after receiving anti-HIV mAb infusion. One to one counseling will be routinely performed.

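### The 7-day solicited list asks about malaise but not fatigue, and about no eye symptom, although the protocol's own safety history names both; a cheap improvement to consistent ascertainment in week 1

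*Protocol*

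**What the plan says.** Section 6.2.11.1 defines the solicited events: "Solicited adverse events in this study include presence of feverishness, chills, headache, nausea, vomiting, malaise, myalgia and arthralgia occurring in the first 7 days" after infusion, together with infusion-site reaction and extravasation effects. On method it says: "Solicited adverse events will be collected prospectively by structured interviews on infusion and post-infusion follow up visits". Under Section 6.2.11.2, other events are picked up by an open question at follow-up visits. Section 6.1.4 adds a review of interim history and concomitant medication at each visit.

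The safety history reads as follows.

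- 3BNC117 (Section 3.3.4): "mild transient myalgia, fatigue and headache were the most commonly reported adverse events".
- 10-1074 (Section 3.4.4): "Most common reported adverse event reported to data was fatigue".
- Section 12 repeats myalgia, fatigue and headache for anti-HIV-1 antibodies, including both products.
- Eyes, 3BNC117 (Section 12): "Sixty-eight participants have received 3BNC117 to date, and 12 participants reported mild ophthalmic complaints" during follow-up, all resolving without specific treatment.
- Eyes, 10-1074 (Section 12), among 22 recipients: "One participant reported transient and mild dryness in the eyes".

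The first primary outcome (Section 3.6) is: "The rate of signs, symptoms and laboratory abnormalities, in addition to local and systemic reactogenicity adverse events 1 week after" the combination infusion.

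Eye events have provisions of their own: a slit-lamp assessment at screening (6.1.2), prompt referral for ocular signs or symptoms and scheduled examinations at Day 28 in Group 1 or Week 20 in Groups 2 and 3 (6.1.4), an eye-specific criterion for stopping later infusions (6.1.7.2, item 3) and notice to the safety monitoring committee (13.1, item 4).

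**The concern.** Two kinds of event that the protocol itself singles out from earlier human experience are missing from the list that is prompted for. In the 7-day window of the primary safety outcome, fatigue and eye symptoms are recorded if the participant raises them in answer to an open question or during the general history. Headache and myalgia, by contrast, are asked about by name every time.

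Prompted and unprompted items generally have different reporting rates, and unprompted reporting depends more on the participant and the interviewer. A low week-1 rate of fatigue or eye symptoms would then be hard to read: it could mean few events or little prompting. In small arms a single participant moves the rate visibly.

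For eye symptoms there is a second consequence. The protocol makes them relevant to referral and to continued dosing, yet writes in no prompt for them between doses in Groups 2 and 3.

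**Working it through.** **1. Match the list against the history.**

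| Prior event | Source | Prompted by name in 6.2.11.1? |
|---|---|---|
| Myalgia (3BNC117) | 3.3.4 | Yes |
| Headache (3BNC117) | 3.3.4 | Yes |
| Fatigue (3BNC117) | 3.3.4 | No; malaise is |
| Fatigue (10-1074, commonest) | 3.4.4 | No; malaise is |
| Eye itching, redness, tearing (3BNC117) | 12 | No |
| Eye dryness (10-1074) | 12 | No |

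Two of the three commonest 3BNC117 events are prompted by name. The one commonest 10-1074 event is not.

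**2. Timing of the eye examinations in Groups 2 and 3.** Infusions are at Weeks 0, 8 and 16 (Section 7.1). The scheduled examination is at Week 20, which is 20, 20 − 8 = 12 and 20 − 16 = 4 weeks after the three doses. It falls after the decisions to give doses two and three. In Group 1, Day 28 is also outside the 7-day window. Between doses in Groups 2 and 3, the referral rule and the eye criterion for stopping therefore come into play only if a participant mentions a symptom or staff notice a sign.

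**3. The plan's own safety figures.** Section 8.2 gives upper 95% limits at zero events of 46% (n = 6) and 19% (n = 18). With 1 − 0.025^(1/n):

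- n = 6: 0.459
- n = 18: 0.185

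Both reproduce and neither is in dispute. They show the scale: one participant is 1/18 = 5.6 percentage points in the pooled active arm and 1/6 = 16.7 in placebo.

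**4. What the eye history can and cannot give.**

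- Rate: 12/68 = 17.6%, exact (Clopper-Pearson) 95% interval 9.5% to 28.8%.
- If it carried over to 18 active participants: 18 × 0.1765 = 3.2 with a complaint; chance of at least one = 1 − (1 − 0.1765)^18 = 97%.
- If only a fraction were recorded (an assumption; the protocol gives no such fraction): 75% gives 2.4 expected and a 92% chance of at least one; 50% gives 1.6 and 81%; 25% gives 0.8 and 56%.

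These are numbers of reports over whole follow-up. Section 12 gives neither the timing of the 12 complaints nor the way they were elicited, so neither the week-1 count nor the number an open question would miss can be derived. For fatigue the protocol gives no rate at all.

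**The case against.** The strongest reply is that little is lost. Myalgia, headache and infusion-site effects are prompted, and malaise overlaps with fatigue. The primary outcome in Section 3.6 covers signs and symptoms generally, so a volunteered complaint counts. Each follow-up visit takes an interim history. Eye effects have examinations, prompt referral, a stopping criterion and committee notice, and the Day 28 examinations in Group 1 are part of the condition for opening Group 2 (Section 4). The wording of 6.2.11.1 may leave the list open, and Appendix B and the interview form are not in the copy at hand.

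Most of this stands, and it limits the point to sensitivity. It does not remove it. Malaise is a different term from the one the protocol uses throughout its safety history. The eye provisions act once a symptom or sign is known; they do not elicit it. If the form already asks these items, 6.2.11.1 should say so.

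Three stronger readings are tempting and not supported.

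- That the primary outcome leaves these events out: Section 3.6 does not restrict it to solicited items.
- That about three eye events would be missed in week 1: the 3.2 and the 97% are expected reports over full follow-up, not missed events. They come from data pooling doses and HIV status, in which Section 3.3.4 says no causal link was established.
- That the placebo comparison is distorted: both blinded arms are questioned alike (6.2.2) and the analysis is descriptive and hypothesis generating (8.1). Even 3/18 against 0/6 gives a two-sided Fisher p of 0.55.

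**Conclusion.** The point holds as a cheap improvement to data collection. Section 6.2.11.1 does not prompt by name for fatigue, a leading prior event of both antibodies, or for any eye symptom, despite 12 of 68 earlier 3BNC117 recipients having mild complaints. Between doses in Groups 2 and 3, the protocol's eye rules rest largely on such symptoms being mentioned.

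The consequence is lower sensitivity and less even ascertainment of the week-1 rate. Its size cannot be computed from the documents; all that can be said is that each unreported active participant shifts the pooled rate by 5.6 points.

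The conclusion assumes that the interview follows the list as printed and that the Time of Events Schedule (Appendix A, not in the copy at hand) adds no eye examination beyond those in Section 6.1.4.

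**What to change.** In Section 6.2.11.1, add 'fatigue' and 'eye symptoms (itching, redness, tearing, dryness)' to the solicited systemic events. Keep the existing window of 7 days after each infusion and use the same structured interview and grading. Check that Appendix B has a grading row for each new item. Later eye symptoms stay under the existing unsolicited-event, referral and examination provisions, so this does not become solicitation over the whole follow-up.

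Cost: two more interview items with their case report form fields, and some additional grade 1 reports in both arms. No visit, procedure, dose or clinical rule changes.
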